### **Secondary objectives:**

- To evaluate how estimated PV (ePV) and estimated total blood volume (TBV) assessments on days 1 and 3 (by established measures such as Nadler's formula or Metropolitan Life Tables) predict measured PV (mPV; as assessed by FAST methodology) and measured TBV (mTBV; calculated from mPV and measured hematocrit) at these time points. Simple linear regression models will be generated and potentially adjusted for relevant confounders.
- To evaluate how a clinical evaluation (including a reasonable subset of the variables age, gender, BMI, hematocrit, edema grade, presence of pulmonary rales, presence of jugular venous congestion, arterial blood pressure, NYHA stage, respiratory rate) on days 1 and 3 predicts mPV and mTBV at these time points. Optimal linear models will be chosen by comparing the results of different variable selection models for the corresponding linear model (backward selection based on p-Values and Akaike Information Criterion, best subset selection etc.).
- To evaluate whether eGFR calculation by the CKD-EPI formula on days 1 and 3 provides an accurate estimate of measured GFR (mGFR; by assessed by FAST

methodology) in heart failure patients undergoing active fluid management. Simple linear regression models will be generated and potentially adjusted for relevant confounders.

- To evaluate whether patients with a low mGFR/eGFR ratio on days 1 and 3 are at higher risk of developing AKI within the following 48-72 hours. Logistic regression models will be generated and potentially adjusted for other relevant confounders.
- To evaluate whether ranges of mPV (low mPV, normal mPV, high mPV) and/or mTBV (low mTBV, normal mTBV, high mTBV) on days 1 and 3 are associated with subjectively reported symptoms (PGA, dyspnea, dizziness, nausea) determined using patient symptom assessment sheets within the following 24-48 hours. Logistic regression models will be generated and potentially adjusted for other relevant confounders. Associations will be assessed by chi-square interaction tests and by Spearman's correlation coefficient.

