- To evaluate whether ranges of mPV (low mPV, normal mPV, high mPV) and/or mTBV (low mTBV, normal mTBV, high mTBV) on days 1 and 3 are associated with subjectively reported symptoms (PGA, dyspnea, dizziness, nausea) determined using patient symptom assessment sheets within the following 24-48 hours.

- 
- To evaluate whether patients with low mPV or low mTBV on day 1 or on day 3 are at risk of developing low-output complications within the next 24-48 hours (subjectively reported dizziness/nausea, PGA, hypotension, need for iv-fluid therapy).
  - To evaluate whether patients with a high mPV or a high mTBV on day 1 and/or day 3 are at risk of being refractory to diuretic therapy (e. g. require dosage increases of furosemide/torsemide, require ultrafiltration/RRT within the next 24-48 hours, fail to improve subjectively in PGA and dyspnea scales).
  - To evaluate whether the time course of ePV and eTBV from day 1 to day 3 adequately reflect the time course of mPV and mTBV at these time points.
  - To evaluate whether the change of mPV and mTBV from day 1 to day 3 is predictive of length of stay, dialysis/ultrafiltration requirement, or rehospitalization within 30 days, or mortality.
  - To evaluate whether the time course of mGFR from day 1 to day 3 correlates temporally with or predicts the time course of eGFR within the next 24-48 hours.
  - To evaluate (by an adjudication committee) whether clinical decision making would have been affected by adding FAST GFR and PV measurements to clinical routine including the following questions:
    - Would FAST GFR and PV measurements have changed clinical management overall?
    - Would the FAST GFR and PV measurement on day 1 have led to applying a different diuretics dosage between day 1-3?
    - Would the FAST GFR and PV measurement on day 3 have led to applying a different diuretics dosage between day 3-5?
    - Would the FAST GFR and PV measurement on day 1 have led to choosing dialysis/ultrafiltration instead of diuretics escalation between day 1-3?
    - Would the FAST GFR and PV measurement on day 1 have led to choosing diuretics escalation instead of dialysis/ultrafiltration between day 1-3?
    - Would the FAST GFR and PV measurement on day 3 have led to choosing dialysis/ultrafiltration instead of diuretics escalation between day 3-5?
    - Would the FAST GFR and PV measurement on day 3 have led to choosing diuretics escalation instead of dialysis/ultrafiltration between day 3-5?

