### 4.3 Secondary variables

#### 4.3.1 Efficacy

- Estimated PV (by Kaplan-Hakim's formula, see chapter 7.2) and measured PV (assessed by FAST methodology) on days 1 and 3
- Estimated TBV (by Nadler's formula, see chapter 7.2) and measured TBV (mTBV: calculated from mPV and measured hematocrit, see chapter 7.2) on days 1 and 3
- Estimated GFR (CKD-EPI formula, sMDRD, Cystatin C formula, and Creatinine-Cystatin C formula, see chapter 7.2) and measured GFR (assessed by FAST methodology) on days 1 and 3 in heart failure patients undergoing active fluid management
- Development of AKI within 72 hours after day 1 and 48 hours after day 3 respectively
- Current level and level within last 24 hours of well-being, dyspnea, dizziness, nausea reported on day 1 and day 3
- Subjectively reported symptoms (PGA, dyspnea, dizziness, nausea) determined using patient symptom assessment sheets within the following 24 and 48 hours on day 1 and following 24 and 48 hours on day 3
- Low-output complications within the next 24 and 48 hours (e. g. subjectively reported dizziness/nausea, PGA, hypotension (Systolic <100, diastolic <60mmHg), need for iv-fluid therapy) at day 1 and within the next 24 and 48 hours at day 3
- Risk of being refractory to diuretic therapy (e. g. require dosage increases of furosemide/torsemide, require ultrafiltration/RRT within the next 24-48 hours, fail to improve subjectively in PGA and dyspnea scales) within 24 and 48 hours on day 1 and day 3

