To evaluate whether eGFR calculation by the CKD-EPI formula and sMDRD formula on days 1 and 3 provides an accurate estimate of measured GFR (mGFR; assessed by FAST methodology) in heart failure patients undergoing active fluid management, linear regression models with the measured value at a given day as dependent variable and the estimated version as independent variable will be generated. The models will be adjusted for mPV and mPVS. Further, Bland-Altman plots will be generated comparing the estimated and measured parameters separately for day 1 and day 3. The defined limits of agreements are  $\pm 6\text{ml/min}$ . Diagnostic accuracy including frequencies of values between 15% and 30% of the measured value will be determined as mentioned before.

To evaluate whether patients with a low mGFR/eGFR ratio on days 1 and 3 are at higher risk of developing AKI within the following 72 (day 1) and 48 (day 3) hours, logistic regression models with the AKI status as dependent variable and mGFR/eGFR ratio as independent variables will be generated. The models will be adjusted for mPVS, mTBVS. Three different versions of the mGFR/eGRF ratio will be evaluated: ratio  $< 1$ ; ratio  $<$  first quartile; ratio as continuous parameter.

To evaluate whether ranges of mPVS (low mPVS ( $< -10\%$ ), normal mPVS ( $-10$  to  $+10\%$ ), high mPVS ( $> +10\%$ )) and/or mTBVS (low mTBVS ( $< -10\%$ ), normal mTBVS ( $-10$  to  $+10\%$ ), high mTBVS ( $> +10\%$ )) on days 1 and 3 are associated with subjectively reported symptoms (current PGA  $> 15$ , current dyspnea  $> 15$ , current dizziness  $> 15$ , current nausea  $> 15$ ) determined using patient symptom assessment sheets within the following 24-48 hours, a logistic regression

---

model with occurrence of symptoms (PGA, dyspnea, dizziness, nausea) as dependent variable and the categorized measured value (mPVS, mTBVS) as independent variables will be generated. The models will be adjusted for mean arterial pressure.

To evaluate whether patients with low mPVS ( $< -10\%$ ) or low mTBVS ( $< -10\%$ ) on day 1 or on day 3 are at risk of developing low-output complications within the next 24-48 hours (subjectively reported dizziness  $> 15$ , nausea  $> 15$ , PGA  $< 25$ , hypotension (Systolic  $< 100$ , diastolic  $< 60$  mmHg), need for iv-fluid therapy), logistic regression models using mPVS and mTBVS as independent variables will be used.

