## 8 Changes from the protocol

In general, no variable selection will be done in the regression models due to limited sample size. Rather clinical expertise regarding the most important explanatory variables will be used to determine a fixed, hierarchical set of possible covariates.

The mPVS and mTBVS are used to determine patients with low, normal or high PV and TBV and thus, the status will be defined based on established estimation formulas for ideal PV and TBV incorporating weight and/or height.

The analysis of the time course of estimated and measured PV and TBV via t-tests was replaced by Bland-Altman-analyses since these analysis better reflects the underlying question of clinically equivalent measurements. Further, the curve characteristics (e.g. times when maximal and minimal volumes are reached and the areas under the curve) based on only few time points were deemed to be of minor meaningfulness.

Haemoglobin for estimating plasma volume changes by Strauss formula and cystatin C values to estimate Glomerular Filtration Rate were also recorded during the study and will also be utilized for the analysis in the respective estimation formulas.

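### For the three-level volume-symptom question the SAP names only a model adjusted for mean arterial pressure, which may understate the overall association; the model without pressure should be reported beside it.

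*SAP*

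**What the plan says.** SAP 7.7.1 asks whether categories of mPVS and mTBVS on days 1 and 3 (cut at -10% and +10%) are associated with symptoms over the following 24-48 hours. It specifies a logistic "model with occurrence of symptoms (PGA, dyspnea, dizziness, nausea) as dependent variable and the categorized measured value (mPVS, mTBVS) as independent variables". One covariate is named: "The models will be adjusted for mean arterial pressure". The day of the MAP reading and the reason for choosing it are not given.

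The next paragraph of 7.7.1 turns to low volume and low-output complications. Its outcomes are dizziness, nausea, PGA below 25, hypotension and need for intravenous fluid. For these, "logistic regression models using mPVS and mTBVS as independent variables will be used", and no adjustment for MAP is named. SAP 1.1 words the same objective as whether patients with low volume "are at risk of developing low-output complications within the next 24-48 hours (subjectively reported dizziness/nausea, PGA, hypotension, need for iv-fluid therapy". SAP 4.3.1 gives the variable as "Low-output complications within the next 24 and 48 hours (e. g. subjectively reported dizziness/nausea, PGA, hypotension (Systolic <100, diastolic <60mmHg), need for iv-fluid therapy".

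Protocol section 14, under the secondary objectives, says of the symptom question: "Logistic regression models will be generated and potentially adjusted for other relevant confounders". It then adds chi-square tests and Spearman's correlation for the same associations. SAP 7.7.1 does not carry those two analyses over, and SAP section 8, which lists changes from the protocol, does not mention them. On covariates in general, section 8 says: "Rather clinical expertise regarding the most important explanatory variables will be used to determine a fixed, hierarchical set of possible covariates".

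**The concern.** The question is whether volume status goes with symptoms. If low volume produces dizziness or nausea partly by lowering blood pressure, a model that holds pressure fixed shows only the rest of that link. Where most of the link runs through pressure, the adjusted odds ratio would sit near 1 although the association asked about is present.

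SAP 7.1 gives the aim as generating hypotheses for phase III, so the practical risk is that a usable signal is read as absent. There is also a problem of reading the results: dizziness and nausea above the same cutoff would be reported against volume status with MAP in one paragraph and without it in the next, with no explanation of the difference.

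**Working it through.** The plan states no effect size, event rate or power for these models, so there is no figure of its own to reproduce. The check has two parts.

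**1. The texts side by side**

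| Place | Role of blood pressure | Unadjusted result for the three-level symptom question? |
|---|---|---|
| SAP 7.7.1, symptom paragraph | Covariate (MAP, day not stated) | None named |
| SAP 7.7.1, next paragraph; 1.1; 4.3.1 | Hypotension is an outcome that low volume may lead to | No: low volume only, with dizziness, nausea and PGA <25; no dyspnea >15 outcome |
| SAP 7.7.1, clinical-evaluation models | MAP is a candidate predictor of mPV and mTBV | Not applicable |
| SAP 4.1 | MAP is a baseline characteristic | Not applicable |
| Protocol section 14 | Not named; optional adjustment for confounders | Yes: chi-square and Spearman, not carried into SAP 7.7.1 |

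The SAP thus expects pressure and volume to be related and treats low pressure as a possible result of low volume. It does not settle whether the MAP covariate is an intermediate, a confounder or both.

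**2. How far the two odds ratios could differ**

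Every input here is an assumption; none comes from the documents.

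- Volume status is normal with SD 15 points. With the SAP cutoffs of -10% and +10%, the low share is Φ(-10/15) = 0.252, the normal share 0.495 and the high share 0.252.
- Standardised MAP = ρ × standardised volume + √(1 - ρ²) × noise, with ρ from 0 to 0.6. Volume is taken to drive MAP, with no confounder.
- Symptom log-odds = -1.0 + ln(direct OR) × low - b × standardised MAP, with b = 0.3, 0.7 or 1.0 (odds ratio 1.35, 2.01 or 2.72 per SD lower MAP).
- 400,000 simulated subjects per scenario, so the results show what each model estimates, not its precision at 50 patients.

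Low-versus-normal odds ratio at b = 0.7, given as without MAP / with MAP:

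| Direct OR | ρ = 0 | ρ = 0.2 | ρ = 0.4 | ρ = 0.6 |
|---|---|---|---|---|
| 1.0 | 1.00 / 1.00 | 1.20 / 1.02 | 1.39 / 1.00 | 1.65 / 1.00 |
| 1.5 | 1.45 / 1.50 | 1.69 / 1.49 | 2.01 / 1.51 | 2.41 / 1.51 |
| 2.0 | 1.90 / 2.02 | 2.19 / 1.99 | 2.62 / 2.01 | 3.16 / 2.03 |

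Share of the log odds ratio removed = 1 - ln(OR with MAP) / ln(OR without MAP). For direct OR 1.5 and ρ = 0.4 this is 1 - ln 1.51 / ln 2.01 = 1 - 0.412/0.698 = 41%. Over all three values of b and ρ from 0.2 to 0.6, the share is 8-60% when there is a direct effect (OR 1.5 or 2.0), and essentially all of it when there is none.

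At ρ = 0 nothing is removed. The adjusted log odds ratio is then 2-20% larger, because an odds ratio changes when a predictive covariate is added even if that covariate is unrelated to the exposure.

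**The case against.** **MAP may be a legitimate covariate.** Listing hypotension beside dizziness and nausea makes them parallel outcomes; it does not say that one produces the other. The hypotension in question develops over the next 24-48 hours, whereas SAP 4.1 lists MAP as a baseline characteristic, and a reading taken at or before the volume measurement need not be an intermediate. In decompensated heart failure MAP may also reflect pump function and drugs, which makes it a plausible confounder of the kind that the protocol allows. Whether volume relates to symptoms beyond a routinely measured pressure is a fair question in this trial. All of this stands, and it is why the adjusted model should be kept.

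**Unadjusted results exist elsewhere.** A reader might infer that no unadjusted result is planned at all. The documents do not support that. The protocol's chi-square and Spearman analyses have not been formally withdrawn. The low-output models name no MAP adjustment for dizziness, nausea and PGA, although the SAP does not say whether these are modelled separately or as one composite. The models for refractoriness to diuretics include failure to improve in PGA and dyspnea, again without MAP. None of these gives the low/normal/high comparison or the dyspnea >15 outcome in the SAP's regression form, so a gap remains, but a narrower one.

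**The size is built in.** The simulation assumes that volume drives MAP and that there is no confounding, so attenuation for ρ above 0 is guaranteed. Precision is also poor. If, say, 4 of 12 low-volume patients and 8 of 38 others had a symptom, the standard error of the log odds ratio would be √(1/4 + 1/8 + 1/8 + 1/30) = 0.73. The 95% interval would span a factor of exp(1.96 × 0.73) ≈ 4.2 either way, so many of the differences above could not be seen in 50 patients. This too stands; the case for the change is one of interpretation.

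**Conclusion.** The point holds in a limited form. For the three-level volume-symptom question, SAP 7.7.1 names only a MAP-adjusted model. Because the SAP itself treats hypotension as a possible consequence of low volume, that model may understate the overall association.

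The amount cannot be derived from the documents. Under the assumptions above it ranges from nothing (volume and MAP unrelated) to essentially the whole low-volume log odds ratio (an effect running only through pressure). The argument is clearest for low volume with dizziness, nausea and PGA, and weaker for high volume and for dyspnea.

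A reader might go further and call the adjustment an error that removes the association. That is not supported: the MAP reading is undated, and MAP may be partly a confounder. The analysis is secondary and, by SAP 7.1, descriptive including its p values, so the primary conclusions on safety and marker stability are untouched. This is a worthwhile improvement of low severity.

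**What to change.** In SAP 7.7.1, for each symptom, report two three-level models side by side:

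- the model without MAP, as the estimate of the overall association between volume status and the symptom;
- the MAP-adjusted model, labelled as the association given blood pressure.

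State that the MAP value is the reading taken at or before the volume measurement on the same study day, and give the reason for including it. Protocol Table 6 already schedules supine morning pressure on days 1-5, so no new data are needed. Add a note that the gap between the two odds ratios is not to be read as the share acting through pressure, since confounding and the behaviour of odds ratios under adjustment also contribute. In section 8, record whether the protocol's chi-square and Spearman analyses for this objective are kept or dropped.

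The cost is one extra model per symptom, fitted wherever the adjusted one is planned, and a few sentences of text. The model without MAP has one parameter fewer, which helps with 50 patients. The downside is two estimates per symptom to present and explain in an already long list of secondary analyses.

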## 5.1 Inclusion criteria

- Written informed consent indicating that they understand the purpose of and procedures required for the study and are willing to participate in the study prior to any study related measures present
- Hospitalized patient with acute decompensated heart failure, diagnosed on the basis of the presence of at least one symptom (dyspnea, orthopnea, or edema) and one sign (rales, peripheral edema, ascites, or pulmonary vascular congestion on chest radiography) of heart failure.
- Subject:  $\geq 18$ . Male with female partners of childbearing potential gave agreement to practice abstinence or use condoms from enrollment through 90 days after administration of the last dose of study drug present.
- A female subject is eligible to enter the study if she is:
  - Not pregnant or nursing
  - Of non-childbearing potential (i.e., post-menopausal defined as having been amenorrheic for at least 1 year prior to screening, or has had bilateral tubal ligation at least 6 months prior to administration of study drug or bilateral oophorectomy or complete hysterectomy)
  - If of childbearing potential, must have a negative urine or serum pregnancy test prior to drug administration and be using a highly effective means of contraception during study participation and until 1 month after the last dose of study drug. Highly effective contraception methods include:
    - Total abstinence (when this is in line with the preferred and usual lifestyle of the subject. Periodic abstinence (e.g., calendar, ovulation, symptothermal, post-ovulation methods) and withdrawal are not acceptable methods of contraception
    - Combination of any two of the following (i+ii or i+iii, or ii+iii):
      - (i) use of oral, injected or implanted hormonal methods of contraception or other forms of hormonal contraception that have comparable efficacy (failure rate  $< 1\%$ ), for example hormone vaginal ring or transdermal hormone contraception.
      - (ii) placement of an intrauterine device (IUD) or intrauterine system (IUS)
      - (iii) barrier methods of contraception: condom or occlusive cap (diaphragm or cervical/vault caps)
    - In case of use of oral contraception women should have been stable on the same pill for a minimum of 3 months before taking study treatment
- 

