## 5.2 Exclusion criteria

- New or ongoing myocardial infarction or instable angina present at the time of planned study inclusion.

- Patient shows evidence of severe infection other than pneumonia, or active internal bleeding (characterized by recent decrease of blood hemoglobin concentration by more than 2 g/dl).
- Patient experiences new onset atrial fibrillation.
- Patient has an elective surgery planned during the 30 days they are enrolled in the study.
- Patient has a psychiatric disease or a history of illicit drug use that would prohibit them from complying with study requirements
- Prior exposure to VFI present.
- History of any clinically significant allergic or negative reactions, side effects, or anaphylaxis to fluorescent dyes, or dextran molecules present.
- Patient requires intravenous vasodilators or inotropic agents (other than digoxin or digitoxin) for heart failure.
- Patient undergoes chronic dialysis (for example peritoneal or hemodialysis) treatments.
- Patient is in cardiogenic shock or on vasopressors.
- Hypotension as defined by blood pressure  $\leq 90$  systolic and/or  $\leq 50$  mm Hg diastolic exists.
- Patients suffering from significant non-cardiac diseases of other organ systems (e. g. Malignancies, significant neurological diseases).
- Patient does not have a working telephone.
- Patient is a pregnant or nursing (lactating) women, where pregnancy is defined as the state of a female after conception and until the termination of gestation, confirmed by a positive human chorionic gonadotropin (hCG) laboratory test.
- Lack of willingness to storage and disclosure of pseudonymous disease data in the context of the clinical trial present.
- Subject has a participation in another interventional clinical trial during this study or within 30 days (or longer) before entry into this trial (as a minimum; 5 x elimination half-life / terminal elimination of an IMP).
- Subject is legally detained in an official institution.
- Subject is dependent on the sponsor, the investigator or the trial sites.

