### Exclusion criteria

- New or ongoing myocardial infarction or instable angina present at the time of planned study inclusion.
- Patient shows evidence of severe infection other than pneumonia, or active internal bleeding (characterized by recent decrease of blood hemoglobin concentration by more than 2 g/dl).
- Patient experiences new onset atrial fibrillation.
- Patient has an elective surgery planned during the 30 days they are enrolled in the study.
- Patient has a psychiatric disease or a history of illicit drug use that would prohibit them from complying with study requirements
- Prior exposure to VFI present.
- History of any clinically significant allergic or negative reactions, side effects, or anaphylaxis to fluorescent dyes, or dextran molecules present.
- Patient requires intravenous vasodilators or inotropic agents (other than digoxin or digitoxin) for heart failure.
- Patient undergoes chronic dialysis (for example peritoneal or hemodialysis) treatments.
- Patient is in cardiogenic shock or on vasopressors.
- Hypotension as defined by blood pressure < 90 systolic and/or < 50 mm Hg diastolic exists.
- Patients suffering from significant non-cardiac diseases of other organ systems (e. g. Malignancies, significant neurological diseases).
- Patient does not have a working telephone.

- 
- Patient is a pregnant or nursing (lactating) women, where pregnancy is defined as the state of a female after conception and until the termination of gestation, confirmed by a positive human chorionic gonadotropin laboratory test.
  - Lack of willingness to storage and disclosure of pseudonymous disease data in the context of the clinical trial present.
  - Subject has a participation in another interventional clinical trial during this study or within 30 days (or longer) before entry into this trial (as a minimum; 5 x elimination half-life / terminal elimination of an investigational medicinal product).
  - Subject is legally detained in an official institution.
  - Subject is dependent on the sponsor, the investigator or the trial sites.

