To evaluate whether patients with a high mPVS ( $> +10\%$ ) or a high mTBVS ( $> +10\%$ ) on day 1 and/or day 3 are at risk of being refractory to diuretic therapy (defined as any dosage increases of furosemide i.v. dose equivalent, adding thiazide after day 1, require ultrafiltration/RRT within the next 24-48 hours, fail to improve subjectively in PGA and dyspnea scales, fail of mean weight loss during the study period Day 1-Day 5 of at least 0,5 kg/d) logistic regression models using mPV and mTBV as independent variables will be used.

To evaluate whether the changes of ePV (using relative and absolute change as well as the Strauss' formula) and eTBV (using relative and absolute change) from day 1 to day 3 adequately reflects the changes of mPV and mTBV Bland-Altman plots will be generated. These plots will be analysed exploratory, since no appropriate values for limits of agreements are available. The amount of values within 10% and within 30% of the measured values will also be determined. In addition, the diagnostic test accuracy including 95% confidence interval as proposed by Obuchowski will be calculated.

To evaluate whether the change of mPV and mTBV and changes of mPVS and mTBVS from day 1 to day 3 as well as the mPVS and mTBVS on Day 1 and Day 3 is predictive of the remaining length of stay at the given day (i.e. remaining length of stay starting with day 1 or with day 3), dialysis/ultrafiltration requirement, or rehospitalization within 30 days, or mortality, linear (remaining length of stay), logistic (dialysis/ultrafiltration, rehospitalization within 30 days) or Cox-regression models (mortality) will be utilized using changes of mPV and mTBV from day 1 to day 3 (first model), changes of mPVS and mTBVS from day 1 to day 3 (second model), and mPVS and mTBVS at day 1 (third model) and day 3 (fourth model) as independent variables.

To evaluate whether the percentage changes of mGFR from day 1 to day 3 ( $< 0$  vs.  $\geq 0$ ; continuous) predicts the percentage changes of eGFR from day 2 to day 4 (CKD-EPI formula only;  $< 0$  vs.  $\geq 0$ ; continuous), a logistic as well as a linear regression model will be used.

The same will be done to investigate the changes in eGFR from day 1 to day 3 (all formulas) as the dependent variable. Further, exploratory Bland-Altman plots without predefined limits of agreement will be created.

To evaluate whether patients with a high PVS or TBVS on Day 1 ( $> +10\%$ ) and a decreasing PVS

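### SAP 7.7.1 scores low-output complications as absolute levels with no index-day rule, so a state already present when plasma volume is measured counts as one that developed afterwards

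*SAP*

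**What the plan says.** SAP 7.7.1 poses the low-output question as one of new events: whether patients with low mPVS or mTBVS "on day 1 or on day 3 are at risk of developing low-output complications within the next 24-48 hours". The components there are dizziness >15, nausea >15, PGA <25, hypotension and i.v. fluid need. SAP 4.3.1 gives the same pressure cut-off: "hypotension (Systolic <100, diastolic <60mmHg), need for iv-fluid therapy". For the analysis, "logistic regression models using mPVS and mTBVS as independent variables will be used"; no other term is listed.

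The SAP's exclusion criterion reads "Hypotension as defined by blood pressure < 90 systolic and/or < 50 mm Hg diastolic exists". Protocol 5.2 has the same criterion with ≤90 and ≤50. The two limits differ by the equality sign and should be reconciled, but the point below holds under either.

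The neighbouring symptom-range analysis in SAP 7.7.1 takes current PGA, dyspnea, dizziness and nausea (each >15) over the following 24-48 hours as outcomes. It adjusts for mean arterial pressure only.

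The definition of diuretic refractoriness includes "fail to improve subjectively in PGA and dyspnea scales, fail of mean weight loss during the study period", alongside dose increases, added thiazide and ultrafiltration/RRT. Entry under Protocol 5.1 needs the "presence of at least one symptom (dyspnea, orthopnea, or edema"), so dyspnea is not required.

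**The concern.** The question concerns incidence, but the scoring rule measures prevalence at 24-48 hours. A patient whose pressure or symptom score is past the cut-off on Day 1 and unchanged on Day 2 is counted as having developed a complication after the volume measurement. The symptom-range analysis has the same gap, because a symptom present on the index day and still present a day later is an outcome event.

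At stake is how the result is read. The SAP's aim is to generate hypotheses for phase III. An association between low plasma volume and low pressure or symptoms that coexist with it could be carried forward as evidence that the measurement predicts later complications.

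A smaller related gap is that the refractory definition has no rule for a patient already at the best end of the dyspnea or PGA scale on the index day, who has no room to improve on it.

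**Working it through.** The documents give no event rate or power figure for these outcomes, so there is nothing to reproduce.

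**Step 1: entry limit against outcome cut-off.** Under the protocol, systolic 91-99 or diastolic 51-59 mmHg is eligible and already below the outcome cut-off. Under the SAP the bands are 90-99 and 50-59. This needs no assumption. For Day 3, Protocol 9.1 allows withdrawal of a patient who develops an exclusion criterion, but that refers to the entry limits and leaves the gap open.

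**Step 2: how many patients might be affected (assumed inputs, not trial data).** Take Day 1 systolic S and diastolic D as bivariate normal, SD 20 and 11, correlation 0.6, truncated to S>90 and D>50.

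- Either below: 1 − P(S≥100, D≥60) / P(S>90, D>50)
- Both below: P(90<S<100, 50<D<60) / P(S>90, D>50)

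For means 120/70, the either figure is 1 − 0.739/0.913 = 0.191.

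| Assumed means | Either below | Of 50 | Both below | Of 50 |
|---|---|---|---|---|
| 115/65 | 29.3% | 14.7 | 5.7% | 2.9 |
| 120/70 | 19.1% | 9.5 | 3.3% | 1.6 |
| 125/72 | 14.7% | 7.3 | 2.2% | 1.1 |
| 130/75 | 9.8% | 4.9 | 1.3% | 0.6 |

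**Step 3: effect on the hypotension component.** Let p be the share hypotensive at index, s the share of those still hypotensive at follow-up, and i the rate of new hypotension in the rest. The counted event rate is q = p·s + (1 − p)·i. All values are assumptions.

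*No true effect on new events, different prevalence at index* (p = 0.30-0.40 with low mPVS, 0.15 otherwise; s = 0.6-0.8; i = 0.05-0.10):
- Lowest: q1 = 0.30×0.6 + 0.70×0.10 = 0.250 and q0 = 0.15×0.6 + 0.85×0.10 = 0.175. OR = (0.250/0.750)/(0.175/0.825) = 1.57.
- Highest: q1 = 0.40×0.8 + 0.60×0.05 = 0.350 and q0 = 0.15×0.8 + 0.85×0.05 = 0.1625. OR = (0.350/0.650)/(0.1625/0.8375) = 2.78.
- Among patients free of hypotension at index, the OR is 1.00.

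*True OR 3.0 for new events, equal prevalence at index* (i = 0.10 in the reference group, hence 0.25 with low mPVS; s = 0.8):
- p = 0.20: q1 = 0.16 + 0.80×0.25 = 0.36 and q0 = 0.16 + 0.80×0.10 = 0.24. OR = (0.36/0.64)/(0.24/0.76) = 1.78.
- p = 0.10 gives 2.14 and p = 0.30 gives 1.58.

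**Step 4: is there a rule elsewhere?** SAP 8 announces a fixed, hierarchical set of possible covariates, but none is named for the low-output model. SAP 7.7.2 does use the missing logic for adverse events: they count only if absent before the first VFI dose or worse after it. Index-day symptom levels (SAP 4.3.1) and Day 1-5 supine blood pressure (Protocol Table 6) are collected.

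**The case against.** **The stakes are limited.** These are secondary analyses that the SAP calls purely descriptive, and they do not touch the primary objective. That stands and sets the weight of the point. It does not remove the mismatch between question and scoring.

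**The numbers are assumed.** This also stands. Reading the cut-off as either or both moves the affected share from 10-29% to 1-6%, more than any other input considered. Most patients are free of hypotension at entry in every scenario, and Day 3 is not quantified.

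**A reader might infer that the whole low-output result becomes a cross-sectional association.** The documents do not support that. The composite also includes i.v. fluid need, which is an event, and counting prevalent cases creates a false association only if index-day prevalence differs by mPVS.

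**A reader might also infer that the refractory outcome ignores the index day, and that its association with high volume is diluted or reversed.** That goes too far. Most of its components are changes or events. The wording on PGA and dyspnea may require failure on both scales, so a dyspnea-free patient whose PGA improves need not count. The symptom sheet (Annex D) is not in the available text, and PGA appears as >15 in one analysis and <25 in the next, so the scale's floor and direction cannot be confirmed. Any direction of bias would assume that few symptoms mean low intravascular volume, whereas the protocol hypothesizes that measured volume differs from clinical assessment. Nor do the documents show that patients at their last stable weight on Day 1 are numerous enough to justify restricting the weight-loss component. What remains is a missing floor rule.

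**Conclusion.** The point holds for the low-output outcome and, for the index-day symptom score, for the symptom-range analysis. The gap between the entry limit and the outcome cut-off follows from the text alone. Its size does not: under the assumed distributions about 5-15 of 50 patients are affected if either pressure suffices, and about 1-3 if both are required. The consequence is a false association if index-day hypotension differs by mPVS (odds ratio 1.6-2.8 in the assumed cases, for the hypotension component alone), and otherwise dilution of a true one (3.0 to 1.6-2.1). For refractoriness, only the missing rule for patients at the scale floor is supported. This should be corrected before analysis, but it does not bear on the trial's main conclusions.

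**What to change.** In SAP 7.7.1:

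1. Score each low-output component, and each outcome in the symptom-range analysis, as new only in patients who did not meet it on the index day (Day 1 or Day 3). Report how many already met it.
2. Alternatively, for a component analysed singly, keep all patients and adjust for its index-day value. Entering every index-day value into a composite model is not realistic with 50 patients.
3. State that the composite is formed from the components for which the patient was at risk.
4. State whether the pressure cut-off requires either value or both.
5. For refractoriness, score failure to improve on a scale only in patients symptomatic on that scale on the index day, and say whether PGA and dyspnea must both fail.

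The change is to SAP wording only; the index-day values are already collected. The cost is fewer evaluable patients and events per component, and a composite whose at-risk components vary between patients, which the report should show.
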